This pilot randomized clinical trial uses a unmasked, prospective, parallel group, superiority design.

Participants are allocated 1:1:1 (unstratified) to dyadic CARE, supporter-only CARE, or waitlist control. Assessments are completed via self-report at baseline, post session 1, and 1, 2, and 3 months postbaseline.

7. Objectives

(Specific objectives or hypotheses)

The goal of this protocol is to describe our methods for a pilot randomized clinical trial of dyadic and supporter-only CARE. Our goals are to understand feasibility, acceptability, and preliminarily characterize efficacy. We hypothesize:

H1: Dyadic and supporter-only CARE will be rated as acceptable by survivors and supporters at 1-month follow-up.

H2: Dyadic and supporter-only CARE will lead to increases in survivor and supporter knowledge from baseline to 1-month follow-up.

H3: Dyadic and supporter-only CARE will improve disclosure experiences (i.e., increasing survivor disclosure frequency, reducing supporter negative reactions, increasing supporter responsiveness) at 1-month follow-up compared to waitlist.

H4: Dyadic CARE and supporter-only CARE will improve functional outcomes among survivors (i.e., PTSD, stress, relationship quality) and supporters (i.e., stress, relationship quality) at 3-month follow-up compared to waitlist.

8. Description of trial design

Type of trial

(eg, parallel group, crossover, factorial, single group)

Parallel group, three arm

Allocation ratio

1:1:1

Framework

(eg, superiority, equivalence, noninferiority, exploratory)

Superiority

Methods: Participants, Interventions, and Outcomes

9. Study setting

Description of study settings

Remote

Reference to where list of study sites can be obtained

N/A

10. Eligibility Criteria

Inclusion criteria

Inclusion Criteria (Survivors):

- Age 14+ years
- Can speak/read English or Spanish
- Have access to a Zoom-capable device
- Screened for eligibility within 10 weeks of sexual assault, defined as any unwanted, distressing sexual contact (e.g., unwanted touching, coerced sexual activity, rape)
- Able to attend first study session within 2 weeks of screening
- Elevated PTSD symptoms at screening as operationalized by a Primary Care PTSD Screen score of 2/5 or above
- Able to identify an eligible supporter
- Have a way to receive survey links and complete surveys privately (i.e., without potential device or account access by the supporter)

Inclusion Criteria (Supporters):

- Age 14+ years

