Reference to where other details of the statistical analysis plan can be found, if not in the protocol

Analyses will be conducted with the intent-to-treat sample. As this study is not powered to detect statistical significance, we will examine the direction and magnitude of effects to preliminarily understand efficacy and test significance in an exploratory manner only. Within-group ds will be calculated as the mean-level difference in scores from baseline to follow-up for each condition divided by the standard deviation of change scores. Between-group ds will represent relative change between conditions and will be calculated as the difference between within-group ds.

Acceptability (H1)

We will use descriptive statistics to summarize acceptability ratings among dyads randomized to dyadic or supporter-only CARE. We will use independent-samples t-tests and between-group *ds* to compare acceptability by condition.

Efficacy (H2–4)

We will calculate within- and between-group *ds* to represent mean changes on focal outcomes. We will use the reliable change index to quantify whether change is unlikely to be attributable to measurement error, and we will report odds ratios for differences in percent with reliable improvement by condition. We will also report the percent of participants meeting diagnostic criteria based on the PCL at baseline and 3-month follow-up.

Paired sample t-tests will evaluate mean changes from baseline to follow-up. We will test time-by-condition interactions in random-effects models using maximum likelihood estimation to account for missing data. We will test covariates including relationship type, study clinician, participant age, and prior assault history. We will conduct sensitivity analyses with English and Spanish-language participants separately.

20b. Methods for any additional analyses

(eg, subgroup and adjusted analyses)

We will test moderation and visually examine results across groups as a function of:

- Baseline PTSD severity and PCL score \geq cutoff of 33
- Relationship type (friend, parent, partner, other)
- Caregiver burden (Impact on Friends - Ineffectiveness Subscale)

We will conduct sensitivity analyses in the following samples:

- English speakers only

20c. Analysis population and missing data

Definition of analysis population related to nonadherence (eg, as randomized analysis), and any statistical methods to handle missing data (eg, multiple imputation)

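### Section 20a leaves adjustment for each outcome's own baseline unspecified; adding it is a nearly free precision gain, about 34%, 24% or 13% of variance under stated assumptions.

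*Combined protocol and SAP*

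**What the plan says.** Section 20a (Efficacy, H2–4) sets out two between-arm comparisons.

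- An effect size: "Between-group ds will represent relative change between conditions". It is the difference between two within-group ds, each a mean change from baseline "divided by the standard deviation of change scores".
- A model: "We will test time-by-condition interactions in random-effects models", fitted by maximum likelihood. Neither the time coding nor the treatment of the baseline mean is stated.

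On covariates: "We will test covariates including relationship type, study clinician, participant age, and prior assault history". Section 20b lists "Baseline PTSD severity and PCL score" at or above the cutoff, but as moderators and for PTSD only.

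On purpose, 20a says that "we will examine the direction and magnitude of effects to preliminarily understand efficacy", with significance tests exploratory. The schedule is: "Assessments are completed via self-report at baseline, post session 1, and 1, 2, and 3 months postbaseline". Section 14 plans 60–72 dyads, chosen for feasibility, and section 16a does not stratify. A baseline PCL is visible in the plan to report the percentage "meeting diagnostic criteria based on the PCL at baseline and 3-month follow-up". Section 12 refers to the registry for the other outcomes.

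**The concern.** A difference in mean change subtracts the whole baseline score, which amounts to a regression slope of 1 for follow-up on baseline. When the true slope is below 1, this over-corrects for chance baseline differences and adds noise. Adjusting for the baseline score, or constraining the arms to a common pre-randomisation mean, uses the slope that the data support.

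The planned d is built on raw change, so it stays unadjusted whatever model is fitted. For the model, a time-by-condition interaction normally comes with a condition main effect, which leaves baseline means free. That is the natural reading, although the text does not settle it.

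At stake is the precision of the magnitudes that the pilot sets out to report. With 20–24 unstratified dyads per arm, chance imbalance between two arms is common, and with equal SDs the change contrast carries (1 − ρ) of it into that trial's estimate. The planned d also has a scale problem: its divisor depends on ρ, so the same true effect yields a different d on different outcomes.

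**Working it through.** **Inputs.** From the documents: three arms at 1:1:1 (section 8) and 60–72 dyads (section 14), so n = 20 to 24 per arm. The documents give no SDs and no correlation. Assumed: ρ (baseline to follow-up) = 0.3, 0.5, 0.7; k = follow-up SD / baseline SD, varied from 0.8 to 1.3; complete data. There is no figure in the plan to reproduce.

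**Step 1: variances, in baseline-SD units.**

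- Change contrast (also the month-specific interaction with categorical time and free baseline means): (2/n)(1 + k² − 2ρk).
- Adjusted contrast, with the slope pooled over three arms: (2/n) k²(1 − ρ²) × [1 + 1/(3n − 5)].

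The last factor is the cost of estimating one slope: 1 + 1/55 = 1.018 at n = 20 and 1 + 1/67 = 1.015 at n = 24.

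**Step 2: equal SDs, n = 20.** The ratio is (1 + ρ)/2 × 56/55.

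- ρ = 0.3: 0.650 × 1.018 = 0.662, a 34% reduction.
- ρ = 0.5: 0.750 × 1.018 = 0.764, a 24% reduction.
- ρ = 0.7: 0.850 × 1.018 = 0.865, a 13% reduction.

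A simulation of 40,000 three-arm trials gave 0.662, 0.765 and 0.863. At n = 24 the ratios are 0.660, 0.761 and 0.863. At ρ = 0.5 and n = 20 the SE falls from √0.100 = 0.316 to √0.0764 = 0.276 baseline SD.

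**Step 3: unequal SDs, n = 20.**

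| k | ρ = 0.3 | ρ = 0.5 | ρ = 0.7 |
|---|---|---|---|
| 0.8 | 0.511 (−49%) | 0.582 (−42%) | 0.639 (−36%) |
| 1.0 | 0.662 (−34%) | 0.764 (−24%) | 0.865 (−13%) |
| 1.2 | 0.776 (−22%) | 0.887 (−11%) | 0.984 (−2%) |
| 1.3 | 0.820 (−18%) | 0.928 (−7%) | 1.009 (+1%) |

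Before the slope cost, the change variance minus the adjusted variance is (2/n)(1 − ρk)², which is never negative. Any loss is therefore bounded by the slope cost, 1.8% at n = 20.

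**Step 4: linear time.** The gain from constraining the baseline means then depends on the covariance structure. With visits at months 0, 1, 2, 3 and compound symmetry (equal SDs) it is 40%, 27% and 15% for the three ρ values. With random slopes (illustrative intercept/slope/residual variances 0.5/0.05/0.5 and 0.5/0.1/0.4) it is 18% and 10%.

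**Step 5: chance imbalance.** P(|Z| > 0.3/√(2/n)): 0.3/0.316 = 0.949 gives 34% at n = 20; 0.3/0.289 = 1.039 gives 30% at n = 24. This is for one pair of arms and a 0.3 SD difference.

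**Step 6: scale of d.** With equal SDs the SD of change is √(2(1 − ρ)) baseline SDs. A true effect of 0.5 baseline SD then corresponds to 0.5/1.183 = 0.42, 0.5/1.000 = 0.50 and 0.5/0.775 = 0.65. Simulated means of the planned d at n = 20, with no waitlist change, were 0.44, 0.52 and 0.67, slightly higher through small-sample bias. The adjusted contrast divided by the pooled baseline SD averaged 0.51 at every ρ.

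**The case against.** **The size is unknown and may be trivial.** This stands in part. ρ and the SDs are assumptions. A ratio k above 1 is plausible for PTSD, because section 10 requires elevated symptoms at entry; at k = 1.2 and ρ = 0.7 the gain is 2%. If the unstated model already constrains baseline means, it gains nothing, although the planned d remains unadjusted.

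**It changes no conclusion.** Testing is exploratory and the sample size was set for feasibility. At ρ = 0.5 with equal SDs the 95% half-width goes from 1.96 × 0.316 = 0.62 to 1.96 × 0.276 = 0.54 SD, and both are wide. The imbalance figure is not a separate harm, since the SE already includes it. All of this stands, and it makes the point modest. The plan does make magnitude its output, however, and 1/0.764 = 1.31 means that the gain in this case equals about 31% more dyads.

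**Baseline may not exist for every outcome.** This stands. Section 12 defers to the registry. Section 10 also admits survivors who have not yet told the supporter but plan to, so a baseline score for supporter reactions may be absent in some dyads.

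**Stronger readings that the documents do not support.** A reader might infer that the planned analysis is biased or that adjustment is ruled out. Randomisation protects the contrast, and the covariate list is open. A reader might also take 34/24/13% as a ceiling. It is not: the gain is larger at k = 0.8 and, at ρ = 0.3, 0.5 and 0.7, in the four-visit linear case under compound symmetry (40%, 27% and 15%).

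Finally, a reader might prefer linear time because it uses all visits. That ranks models on variance alone and assumes that the effect grows linearly. If post-session-1 is placed at month 0 (an assumption) and a 0.5 SD effect is present from that visit onward, the five-visit linear contrast at month 3 averages 3 × 0.6/6.8 = 0.265. With time-0 means constrained equal it averages 0.375 (ρ = 0.5, compound symmetry). Constraining post-session-1 would force a visit that follows the first CARE session (section 18b) to be equal across arms.

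**Conclusion.** The point holds as a missed precision gain. Section 20a names no adjustment for the outcome's own baseline and no equal-baseline constraint, and the d is built on raw change. With categorical time or raw change, free baseline means, equal SDs, complete data and 20 per arm, adjustment would cut the variance by about 34%, 24% or 13% at assumed ρ of 0.3, 0.5 or 0.7. Over SD ratios from 0.8 to 1.3 the effect runs from a 49% cut to a 1% rise. Under linear time it depends on the covariance structure. The change is worth making because it costs almost nothing where the baseline is already collected. Scope is limited to H3 and H4 outcomes with a pre-randomisation score; the documents show this for the PCL only. H2 is a within-arm comparison and is not affected.

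**What to change.** In section 20a, for each H3 and H4 outcome with a pre-randomisation baseline score:

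1. State that time is categorical (visits).
2. Either constrain the pre-randomisation baseline means, and only those, to be equal across arms, never post-session-1; or model follow-up scores with condition-by-visit and baseline-by-visit terms. The constrained form keeps dyads that lack a baseline value, so it suits outcomes where some baselines will be missing.
3. Report the adjusted contrast for each CARE arm against waitlist at month 1 (H3) and month 3 (H4), beside the planned between-group d.
4. Divide the adjusted and unadjusted contrasts by one common SD, such as the pooled baseline SD, so that they can be compared. Keep the planned d and state its divisor.
5. List which outcomes have a baseline score.

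The cost is SAP wording, with no new data for outcomes already measured at baseline. The statistical price is about 1.8% of variance at 60 dyads or 1.5% at 72 for one estimated slope, with little gain where ρ is high and the SD rises after baseline.

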- Can speak/read English or Spanish
- Have access to a Zoom-capable device
- Able to attend first study session within 2 weeks of survivor's screening
- Are in contact with the survivor at least once a week
- In the opinion of the survivor, are able to make an independent decision about whether or not to participate in the study
- Have a way to receive survey links and complete surveys privately (i.e., without potential device or account access by the survivor)

Exclusion criteria

Exclusion Criteria (Survivors):

- Active psychosis
- Active suicidal intent

Exclusion Criteria (Supporters):

- Perpetrated the sexual assault
- Engaged in severe past-year violence or abuse (as defined by the survivor) against the survivor
- The survivor has not told the supporter about the sexual assault at the time of screening and was not already planning to tell the supporter
- In the opinion of the survivor, relational conflict exists between the survivor and supporter that potentially could be exacerbated by program participation

Eligibility criteria for study centers (if applicable)

N/A

Eligibility criteria for individuals who will perform the interventions

The intervention will be delivered by either the principal investigator (a licensed clinical psychologist) or a staff member trained by the principal investigator

11. Interventions

11a. Interventions for each group with sufficient detail to allow replication, including how and when they will be administered

Intervention

Both telehealth sessions will be 90 min and will be delivered using a slide deck and a script. Sessions will be audio recorded for supervision and fidelity tracking. Clients will be sent an electronic and/or paper workbook following session 1. The clinician will complete a clinical note regarding content coverage and clinical observations. In session 2, the note will document attendance, homework completion, and skills practice. We will also assess homework completion and skills practice via survivor and supporter self-report at 1-month follow-up.

Dyadic CARE

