Dyadic CARE involves two telehealth sessions with a clinician, the survivor, and a supporter of the survivor's choice. Session content uses cognitive-behavioral strategies (e.g., encouraging non-avoidance) to encourage communication and improve supporters' responses in trauma-related conversations. Between sessions, both the survivor and the supporter are instructed to review session content and have guided discussions with the assistance of a workbook.

Supporter-Only CARE

Supporter-only CARE involves two telehealth sessions with a clinician and a supporter of the survivor's choice, without the survivor present. Session content uses cognitive-behavioral strategies (e.g., encouraging non-avoidance) to

encourage communication and improve supporters' responses in trauma-related conversations. Between sessions, both the survivor and the supporter are instructed to review session content and have guided discussions with the assistance of a workbook.

Comparison

Waitlist Control

After completing baseline, participants will be invited to schedule a CARE session in 3 months (i.e., after the completion of all study assessments). The version of CARE received at that point will be selected by the survivor.

Participants will complete self-report assessments at post-session-1, Month 1, Month 2, and Month 3.

11b. Criteria for discontinuing or modifying allocated interventions for a given trial participant

Participants who withdraw consent for participation will no longer be contacted by study staff or sent automated reminders to complete study tasks.

Participants will be withdrawn from the research if at any point if it becomes known that a participant does not meet eligibility criteria for the study, if a participant's condition deteriorates, or if it becomes known that they require a higher level or different type of care that is incompatible with study participation. If this occurs, participants will be asked to withdraw from the study and appropriate referrals will be made.

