We will use an intent to treat analysis, in which participants will be retained in the group to which they were originally randomized. Outcome data from all participants will be included in analyses. We will also explore the use of randomization-based efficacy estimators (White, 2005).

Methods: Monitoring

21. Data monitoring

21a. Data monitoring committee

Composition of data monitoring committee (DMC)

N/A

Summary of its role and reporting structure

N/A

Statement of whether it is independent from the sponsor and competing interests

Reference to where further details about its charter can be found, if not in the protocol

N/A

Alternatively, an explanation of why a DMC is not needed

Given that this is a pilot trial of an intervention with minimal risks, we will not retain a data monitoring committee.

21b. Description of any interim analyses and stopping guidelines

Including who will have access to these interim results and make the final decision to terminate the trial

No interim analyses will be conducted.

We will employ the following stopping rule for the clinical trial: if there is clear evidence of harm. Although we do not expect any physical harms or serious psychological harms beyond minimal distress, we have several procedures for monitoring harm from the intervention, including asking participants to contact us if they experience any adverse events, offering additional resources to those with very high levels of mental health symptoms and problem drinking that we identify through data monitoring, and providing resources after baseline and at every follow-up time point. We do not expect there to be overwhelming evidence of the harm of the intervention, but we will monitor this and stop the trial if this is indicated. We also do not expect that there will be no likelihood of demonstrated treatment benefit (futility) for the intervention as compared to control.

22. Harms

Plans for collecting, assessing, reporting, and managing solicited and spontaneously reported adverse events and other unintended effects of trial interventions or trial conduct

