All participants will be fully informed of how to contact the investigators and/or the UW IRB to report complaints or adverse events via explicit instructions in the consent form. The PI and co-I [name] are well-versed in the requirements and procedures for monitoring and reporting adverse events and complaints to the IRB for review. [name] has managed this process as PI of several previous clinical trials and will work closely with Dr.

[name] to provide guidance and consultation in this process. All adverse events will be reviewed by [name] and other members of the treatment team to determine the seriousness of the adverse events. The PI and co-Is have a wealth of experience in managing adverse psychological events both in the context of clinical trials research and clinical practice and are competent to handle any adverse psychological events which may arise. We will follow institutional policies for reporting serious adverse events (SAEs) and adverse events (AEs) to the IRB and OVW. On a daily basis, [name] will be responsible for data and safety monitoring and will provide continuous, close data monitoring. [name] will follow UW's SAE reporting policy in promptly reporting SAEs to the UW Institutional Review Board (IRB) and to OVW. [name] will report all SAEs to the IRBs within 24 hours. A report of all non-serious adverse events will be provided to the IRB yearly. The PI and co-Is will meet twice a year regarding safety and monitoring procedures. This meeting will be used to review any problems in implementing procedures. [name] will also monitor safety data as part of the yearly review. Safety evaluations will include AEs and longitudinal symptom measures. Safety evaluations will also consider factors external to the study, such as scientific or therapeutic developments that may have an impact on the safety of the participants or the ethics of the study.

23. Auditing

Frequency and procedures for auditing trial conduct, if any, and whether the process will be independent from investigators and the sponsor

No auditing will be conducted.

Ethics and Dissemination

24. Research ethics approval

Plans for seeking research ethics committee/institutional review board (REC/IRB) approval

We have obtained ethical approval from the University of Washington IRB.

25. Protocol amendments

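### Adverse events reach the team only if participants make contact, and session contact differs by arm and dyad member, so events may be missed and counts may not be comparable between arms

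*Combined protocol and SAP*

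**What the plan says.** **Adverse-event route.** Section 21b lists several ways of watching for harm. The one specific to adverse events is "asking participants to contact us if they experience any adverse events". Section 22 repeats it through the consent form: "All participants will be fully informed of how to contact the investigators and/or the UW IRB to report complaints or adverse events". The template heading of section 22 asks about solicited as well as spontaneous events, but the text beneath it gives no adverse-event question, checklist or fixed time of enquiry.

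**Other harm information.** Section 21b also mentions "offering additional resources to those with very high levels of mental health symptoms and problem drinking that we identify through data monitoring". Section 22 adds: "Safety evaluations will include AEs and longitudinal symptom measures".

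**Survey schedule.** For the trial as a whole (design paragraph before section 7): "Assessments are completed via self-report at baseline, post session 1, and 1, 2, and 3 months postbaseline". For waitlist (section 11a): "Participants will complete self-report assessments at post-session-1, Month 1, Month 2, and Month 3". The schedule is the same in all arms.

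**Session contact (section 11a).** Both CARE versions have two 90-minute telehealth sessions. The survivor attends them in the dyadic version and not in the supporter-only version. Waitlist dyads are offered CARE only once all assessments are finished. For sessions, "The clinician will complete a clinical note regarding content coverage and clinical observations". The session 2 note is said to cover attendance, homework and skills practice. Adverse-event enquiry is not mentioned for either session.

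**The concern.** When events are recorded only if somebody volunteers them, the count depends on how often people call as well as on how often events happen. That affects every arm. A second problem may sit on top of it. Someone who spends three hours with a clinician (2 × 90 minutes) has an occasion to mention an event that they would not have telephoned about. Someone without sessions does not. Participants and staff are unblinded (section 17a), so nothing in the design evens this out.

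What is at stake is harm monitoring and any later adverse-event table. The only stopping criterion in section 21b is that harm becomes clear. There is no monitoring committee and no interim analysis (sections 21a and 21b), and the treatment team takes part in judging seriousness (section 22). The protocol also foresees relational harm: section 10 excludes supporters where the survivor thinks that the program might worsen conflict between them. A survivor in supporter-only CARE has no session of their own in which to raise such a problem.

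**Working it through.** The documents give no adverse-event rate, capture rate or planned harm comparison, so there is no figure of the plan's to reproduce. The check sets out who has which route, then shows what a difference in routes could do.

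**1. Routes by arm and dyad member, baseline to month 3** (sections 11a, 18a, 21b and 22)

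| | Contact instructions | Surveys | Clinician sessions |
|---|---|---|---|
| Dyadic CARE, survivor | yes | yes | two |
| Dyadic CARE, supporter | yes | yes | two |
| Supporter-only CARE, survivor | yes | yes | none |
| Supporter-only CARE, supporter | yes | yes | two |
| Waitlist, survivor | yes | yes | none |
| Waitlist, supporter | yes | yes | none |

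For supporters the contrast is both CARE arms against waitlist. For survivors it is dyadic CARE against the other two arms.

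**2. Arm size.** Section 14 gives 60–72 dyads, allocated 1:1:1. That is 60/3 = 20 to 72/3 = 24 dyads, or 40 to 48 people, per arm.

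**3. Illustration. All three rates are assumptions.** Let *p* be the true event risk, equal in every arm. Let *s* be the chance that an event is reported spontaneously, and *c* the chance that an otherwise unreported event surfaces in a session and is then recorded.

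- Waitlist recorded rate: *p·s*
- Dyadic CARE: *p·[s + (1 − s)·c]*
- Supporter-only CARE, where *c* applies to half the arm: *p·[s + (1 − s)·c/2]*

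Dividing by the waitlist rate, *p* cancels:

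- Dyadic : waitlist = 1 + *c*(1 − *s*)/*s*
- Supporter-only : waitlist = 1 + (*c*/2)(1 − *s*)/*s*

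| *s* | *c* | Dyadic : waitlist | Supporter-only : waitlist |
|---|---|---|---|
| any | 0 | 1.00 | 1.00 |
| 0.25 | 0.25 | 1.75 | 1.38 |
| 0.25 | 0.50 | 2.50 | 1.75 |
| 0.50 | 0.25 | 1.25 | 1.125 |
| 0.50 | 0.50 | 1.50 | 1.25 |
| 0.75 | 0.25 | 1.08 | 1.04 |
| 0.75 | 0.50 | 1.17 | 1.08 |

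The top of the range is 1 + 0.50 × 0.75/0.25 = 2.50 for dyadic CARE and 1 + 0.25 × 0.75/0.25 = 1.75 for supporter-only CARE.

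**4. In counts.** Take *p* = 0.20, *s* = 0.50, *c* = 0.50, 40 people per arm and at most one event each. True events: 40 × 0.20 = 8.0 in every arm. Expected recorded events:

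- Waitlist: 8.0 × 0.50 = 4.0
- Supporter-only: 8.0 × (0.50 + 0.50 × 0.25) = 5.0
- Dyadic: 8.0 × (0.50 + 0.50 × 0.50) = 6.0

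Half of the waitlist events go unseen, and so do a quarter of the dyadic ones. With counts this small, two events captured differently change the picture.

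**5. With a common question.** If the same questions in the same surveys are the only source for the comparison, the opportunity to report is equal by design. Under equal true risk the expected ratio is then 1.00, provided that survey response and willingness to answer are similar across arms.

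**The case against.** A reader might infer that adverse-event rates by arm are biased and that waitlist events are under-counted relative to CARE. The documents do not support this as a statement of fact, for four reasons.

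- **Sessions are not described as an adverse-event source.** No section says that something noted in a session is logged as an adverse event. If sessions add nothing, the ratio is 1.00. This stands, and it is why the comparability point is conditional.
- **It is not simply CARE against waitlist.** Survivors in supporter-only CARE have no sessions either. This stands. Nor is waitlist without any clinician contact: both dyad members meet the study clinician at the initial appointment (section 26a), and survey reminders come from the clinician in any arm (section 11c).
- **There is a symmetric harm measure.** Symptoms and problem drinking are monitored, safety evaluation includes symptom scores over time, and the surveys run on one schedule. Negative supporter reactions and relationship quality are also measured (H3 and H4 in section 7) and bear on conflict. So the stopping decision does not rest on event counts alone. This stands in part. A score may move after a confrontation or a crisis visit, but none of these measures is described as recording the event. Section 12 refers to the registry for outcomes, so the documents do not show the instruments, and an existing item cannot be ruled out.
- **No comparison of event rates by arm is planned.** Section 20 contains none. This stands, and it confines the consequence to monitoring and any later safety table.

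None of this answers the basic point that a structured enquiry is not described for anyone.

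**Conclusion.** The point holds as a risk of unknown size. The only adverse-event route described is participant-initiated, which may miss events in all arms. Session contact differs by arm and by dyad member, so counts may not be comparable if events noted in sessions are recorded. Shared symptom and drinking monitoring is a partial offset.

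With equal true risk, 25–75% spontaneous reporting and 0–50% session capture of the remainder, the recorded ratio against waitlist runs from 1.0 to 2.5 for dyadic CARE and from 1.0 to 1.75 for supporter-only CARE. These capture probabilities are assumptions, and the lower end applies if sessions yield no recorded events. No single ratio should be quoted as the effect. The change is worth making because it is cheap and strengthens the information behind the only stopping criterion. It alters no sample size, error rate or efficacy analysis.

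**What to change.** Add the same short adverse-event questions, with the same wording and recall period, to the existing month 1, 2 and 3 online surveys for survivors and supporters in all three arms. Section 10 already requires that each member can answer privately from the other, so the channel suits disclosure of conflict within the dyad.

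State in section 22 that any between-arm harm summary uses these answers. Say whether events noted in sessions are logged as adverse events, and list them and spontaneous reports separately, by arm and dyad member. The separate list also covers people who opt out of questionnaires but still receive the intervention (section 11b), whom the survey would miss. Report the number who answered in each arm, since unequal response could bring back some of the imbalance.

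The cost is slightly longer surveys, more events to review and an IRB modification. No additional visits are needed.
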